2.1 Data analysis general information

All analyses will be performed by Novartis. The most recent version of SAS available in the statistical programming environment of Novartis will be used for the analysis.

Part 1 data are defined as all data collected starting from the screening visit up to the day 360 visit date prior to dosing on this day/date. Part 1 data will be presented by two separate groups (inclisiran and placebo). The total column will be presented in all outputs of Part 1 as needed and will be specified in TFL shell document.

Part 2 data analysis will include all data collected starting from after dosing on day 360. Part 2 data will be presented in two separate groups, (1) inclisiran since Day 1 and (2) placebo-to-inclisiran, unless otherwise specified. The column labels for these two groups will be inclisiran-inclisiran and placebo-inclisiran. The total column will be presented in all outputs of Part 2 as needed and will be specified in TFL shell document.

For instances, where it will not be possible to distinguish whether data belong to Part 1 or Part 2, based on the dosing time on the day 360 visit, all data collected from screening up to the day 360 visit will be considered as Part 1 data and all data captured after the day 360 visit (starting from day 360 visit + 1 day) will be considered as Part 2.

Part 1 data analysis will be performed after all participants completed the day 360 visit (Part 1) or discontinued the study prior to the Day 360 visit. For each participant, data collected in the database till the end of study Part 1 (up-to Day 360 visit as mentioned above) will be included in this analysis. Hence the Day 360 visit of a participant will serve as data cut-off date for that participant. All events with start date before or on the cut-off date and for which the end date has not been reached yet or they are ongoing at final visit will be reported as 'ongoing'. The same rule will be applied to events starting before or on the cut-off date and not having a documented end date. The assessment of study primary objective and key secondary objectives will be based on this analysis.

Part 2 data analysis will be conducted after all participants either completed the study or discontinued early.

Both Part 1 and Part 2 analyses will be reported in the CSR. For summary of the analyses that will be performed for Part 1 analysis and Part 2 analysis see Appendix 5.3.

Detailed information regarding DMC analysis will be provided in the DMC charter and a separate DMC SAP/TFL shells.

2.1.1 General definitions

Study day

Study day will be defined as the number of days since the date of first dose of double-blind treatment. The date of first dose of double-blind treatment will be defined as Day 1 and the day before the first dose of study drug will be defined as Day -1.

Novartis	For business use only	Page 18
SAP amendment 4		CKJX839C12301

Therefore, for a particular date, study day will be calculated as follows:

For dates on or after the first date of double-blind treatment,

Study day = Assessment date – Date of first dose of double-blind treatment + 1;

For dates prior to the first date of double-blind treatment,

Study day = Assessment date – Date of first dose of double-blind treatment.

In case, participant has been randomized but has not received double-blind treatment then randomization visit day will be considered as Day 1.

Baseline definition

In general, for both Part 1 and Part 2, baseline value is defined as the last measurement collected on or prior to the first dose of double-blind treatment.

Post-baseline measurement

Post-baseline values are defined as those measurements that were collected after the first dose of double-blind treatment.

When change from baseline is of interest the following formula will be used for each scheduled visit and time-point where baseline and post-baseline values are both available:

Absolute change from baseline = post-baseline value – baseline value.

Percent change from baseline = (post-baseline value - baseline value) / baseline value*100.

Reflexive LDL-C

The endpoints involving LDL-C will use a reflexive LDL-C approach. The calculated LDL-C will be utilized unless triglycerides are greater than 400 mg/dL and/or calculated LDL-C is less than 40 mg/dL, in which case beta quantification LDL-C (i.e., LDL_C directly measured by ultracentrifugation) will be additionally performed and used for the analysis.

VLDL-C

The endpoints involving VLDL-C will follow the same approach as reflexive LDL-C.

Re-derivation of age-strata for mis-stratified participants

If any subject will be mis-stratified for age-group during randomization, collected age of that participant will be used to re-derive the correct age-strata at analysis level and will be used for all analyses, as needed.

Discontinuation visit mapping

For patients who discontinued from the study and come to site for an early exit (EE) visit, the EE visit will be mapped to the next scheduled visit. The mapping details can be found as below:

Novartis SAP amendment 4 For business use only

Confidential

Page 19 CKJX839C12301

Table 2-1 Visit mapping

Status	Last attended sc to	heduled visit prior EE	Mapped visit for EE		
Visit day	Visit name	Visit day	Visit name	Visit day	
Discontinued (Early exit)	1	Day 1	90	Day 90	
Discontinued (Early exit)	90	Day 90	150	Day 150	
Discontinued (Early exit)	150	Day 150	270	Day 270	
Discontinued (Early exit)	270	Day 270	330	Day 330	
Discontinued (Early exit)	330	Day 330	360	Day 360	
Discontinued (Early exit)	360	Day 360	450	Day 450	
Discontinued (Early exit)	450	Day 450	510	Day 510	
Discontinued (Early exit)	510	Day 510	630	Day 630	
Discontinued (Early exit)	630	Day 630	720	Day 720	
Completed			720	Fay 720	

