2.8 Safety analyses

In general, for Part 1 safety analyses, the SAF will be used; for Part 2 safety analysis, the OAS will be used.

Safety summaries will include only treatment emergent adverse events (TEAEs) by Part. For Part 1, TEAEs are defined as adverse events (AEs) starting on or after the first dose of doubleblind treatment or AEs that were present prior to start of double-blind treatment but increased in severity in Part 1. For Part 2, TEAEs are defined as AEs starting after the Day 360 dosing time or AEs that were present prior to the Day 360 dosing time but increased in severity in Part 2. For Part 1, if the AE start date is the same as the date of the first dose of double-blind treatment but the time is not available for comparison, the AE will be considered as treatment but the time is not available for comparison, the AE will be considered as treatment but the time is not available for comparison, the AE will be considered as treatment but the time is not available for comparison, the AE will be considered as treatment but the time is not available for comparison, the AE will be considered as treatment but the time is not available for comparison.

Vital signs values that have complete data and time values will be assigned to pre- or post-dose assessment (as per protocol) based on the actual date/time. For values with missing date/time, the scheduled visit date and time will be used. This rule will be applied to data from scheduled visits only. If a measurement scheduled as pre-dose is actually performed post-dose, or vice versa, the data will not be used for visit/time point summary.

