2.8.3 Laboratory data

Laboratory data consist of hematology, biochemistry, sexual hormones, urinalysis measurements and ADA (see Section 2.8.6). Absolute values and change from baseline will be summarized for continuous laboratory parameters by visit and box plots will also be provided by visit. Frequency table of results for categorical laboratory parameters will be presented by visit. This analysis will be performed by treatment group and Part.

Shift tables using the low, normal, high/low, or high classification (except for eGFR and HbA_{1c} where the categories outlined below will be applied) will be used to compare baseline to the worst on-treatment value by treatment group and Part. All data collected after first dose of

Novartis	For business use only	Page 31
SAP amendment 4		CKJX839C12301

double-blind treatment, from scheduled, unscheduled, and premature discontinuation visits in each part will be used to determine the worst on-treatment value.

The following categories will be used for eGFR and HbA1c:

- For eGFR, the categories will be <30 mL/min/1.73m²; ≥ 30 to <60 mL/min/1.73m²; ≥ 60 to <90 mL/min/1.73m²; and ≥90 mL/min/1.73m².
- For HbA_{1c}, the categories will be <5.7%; $\ge 5.7\%$ to <6.5%; and $\ge 6.5\%$.

The shift table dealing with the fasting plasma glucose parameter will require the lab sample to be taken fasting. Samples taken while the subject was not fasted will not be analyzed.

For selected laboratory tests, the number and percentage of patients meeting the clinically notable criteria at any time, considering all data collected after first dose of double-blind treatment, from scheduled, unscheduled, and premature discontinuation visits, will be summarized by laboratory parameter and treatment group and Part. The worst post-baseline value will be used for this analysis. Notable criteria are defined in Appendix 5.5. Clinically notable criteria will be considered met when both of the following occur:

- Post-baseline value meets the clinically notable criteria.
- Baseline value does not meet the clinically notable criteria.

Furthermore, the number and percentage of participants meeting notable criteria in liver function tests (LFT) will be summarized by treatment and Part considering on-treatment data from scheduled, unscheduled, and premature discontinuation visit. LFT criteria are defined in Appendix 5.5.

The baseline value is the last value prior to the first dose of double-blind treatment.

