2.8.4 Diabetes assessment

Diabetes will be assessed by the analysis of:

- TEAEs,
- Change in glucose-related laboratory values over time,
- Shifts from baseline in glucose control category and,
- Incidence of post-baseline new onset of diabetes.

Note that diabetes related tables dealing with the fasting plasma glucose parameter will require the lab sample to be taken fasting. Samples taken while the subject was not fasted will not be analyzed.

Unless otherwise specified, baseline of fasting plasma glucose will be defined as the average of Screening and Day 1 assessments. If one fasting plasma glucose value is missing (Screening or Day 1), the baseline will be based on the available data. For HbA1c, the Day 1 assessment will be considered as baseline. If missing, then the baseline will be based on the assessment at screening.

Diabetes TEAE

Novartis	Confidential	Page 33 of 48
Clinical Study Report Appendix 16.1.9, v1.0		Study No. CKJX839C12301

Novartis	For business use only	Page 32
SAP amendment 4		CKJX839C12301

New onset/worsening of diabetes will be identified by the search criteria specified in Appendix 5.4. The analysis will be performed for all subjects and then by baseline diabetes status. A participant will be identified as being diabetic at baseline if the medical history notes that the subject is diabetic or the baseline HbA_{1c} value is $\geq 6.5\%$ or the baseline fasting plasma glucose is ≥ 126 mg/dL. This summary will be provided by treatment and Part.

Change in Glucose-related Laboratory Values over Time

This analysis only utilizes laboratory data (fasting plasma glucose and HbA_{1c}). The change from baseline to the last on-treatment observation and the worst on-treatment observation will be summarized by treatment and Part, separately for fasting plasma glucose and HbA_{1c} for all participants and then by baseline glucose control status. Baseline glucose control status will be identified separately for fasting plasma glucose and HbA_{1c} using the values provided in the table below (note that medical history will not be considered for this analysis). Figures will also be created showing change in mean fasting plasma glucose and HbA_{1c} values over time by baseline glucose control status.

Parameter	Baseline Glucose Control Status (Laboratory Values)
Fasting Plasma Glucose	<100 mg/dL
	\geq 100 to <126 mg/dL
	≥126 mg/dL
HbA1c	<5.7%
	\geq 5.7 to < 6.5%
	≥6.5%

Shifts from Baseline in Glucose Control Category

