*No change (Normal to Normal, Impaired to Impaired, and Diabetes to Diabetes), Worsened (Normal to Impaired, Normal to Diabetes, and Impaired to Diabetes), and Improved (Impaired to Normal, Diabetes to Impaired, and Diabetes to Normal) categories will also be summarized. **For post-baseline categories, if the post-baseline two consecutive fasting plasma glucose measurements fall in separate categories, or if only one post-baseline fasting plasma glucose measurement is available, then the post-baseline glucose control category will be defined based on the HbA1c measurement only. If HbA1c value is missing and two consecutive fasting plasma glucose measurements fall in separate categories, the lower category will be used to determine the post-baseline category.

Incidence of Post-baseline New-Onset of Diabetes

The number of participants who shift from no diabetes at baseline to post-baseline new onset of diabetes will be summarized.

The participants with no diabetes at baseline are those who had no medical history of diabetes in the medical history CRFs, had baseline HbA1c <6.5%, and had baseline fasting plasma glucose <126 mg/dL prior to the start of study treatment.

A 4-component analysis will be utilized to detect post-baseline new onset of diabetes. The 4 components are provided below:

- Diabetic TEAEs identified by the SMQ search (see Section 5.4), or
- Post-baseline fasting plasma glucose \geq 126 mg/dL on two consecutive occasions, or
- Initiation of anti-diabetic medication at any time post-baseline, or
- At least one post-baseline HbA1c $\geq 6.5\%$.

The number of participants who have any of the 4 components will be summarized (postbaseline new onset of diabetes) by treatment and Part.

This analysis will be performed separately for participants who had normal and impaired glucose control categories at baseline.

• Subjects with normal glucose control status at baseline are those with all the following:

Novartis	For business use only	Page 35
SAP amendment 4		CKJX839C12301

- No medical history of diabetes.
- HbA1c < 5.7% and fasting plasma glucose < 100 mg/dL at baseline.
- Subjects with impaired glucose control status at baseline are those with all the following:
 No medical history of diabetes.
 - HbA1c ≥5.7% and <6.5% (and fasting plasma glucose<126 mg/dL) or fasting plasma glucose ≥100 mg/dL and <126 mg/dL (and HbA1c <6.5%) at baseline.

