The time to new onset diabetes will also be summarized by treatment and Part. Only participants without diabetes at baseline will be included in the analysis. The time (weeks) to new-onset diabetes will be calculated from the date of the first administration of study drug.

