2.8.5 Vital signs

Absolute values and change from baseline will be summarized for vital sign parameters by visit, time point, treatment group and Part. For SBP and DBP, average of 3 readings will be used for analysis while all 3 readings will be provided in the listing. Baseline and change from baseline in height, weight, and BMI will be assessed with/without using age- and sex-adjusted z-scores and summarized by visit treatment group and Part.

The number and percentage of patients meeting clinically notable criteria at any time, considering all data collected after first dose of double-blind treatment, from scheduled, unscheduled, and premature discontinuation visits will be summarized by treatment group and Part. The worst post-baseline value in each part will be used for this analysis. Notable criteria are defined in Appendix 5.6. Clinically notable criteria will be met when both of the following occur:

- Post-baseline value meets the clinically notable criteria.
- Baseline value does not meet the clinically notable criteria.

The baseline value is the last value prior to and up to Day 1 of the double-blind treatment.

All vital signs data will be listed by treatment group, participant, and visit/time and if clinically notable criteria are met, abnormalities will be flagged.

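### Part 2 new-onset diabetes in the placebo-inclisiran group keeps a pre-treatment risk set and a Day 1 clock, so cases that began on placebo can be counted again and Part 2 onset times run 51.3 weeks longer than time on inclisiran

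*SAP*

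**What the plan says.** SAP 2.1.1 defines baseline once, relative to the start of double-blind treatment: "for both Part 1 and Part 2, baseline value is defined as the last measurement collected on or prior to the first dose". The safety sections repeat that reference.

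- Laboratory (2.8.3): "The baseline value is the last value prior to the first dose of double-blind treatment". Notable values "will be summarized by laboratory parameter and treatment group and Part. The worst post-baseline value will be used for this analysis". A participant counts if a post-baseline value is notable and the baseline value was not. Shift tables are also produced by Part.
- Vital signs (2.8.5): "The baseline value is the last value prior to and up to Day 1 of the double-blind treatment", with the same two-part rule applied within each Part.
- Diabetes (2.8.4): "baseline of fasting plasma glucose will be defined as the average of Screening and Day 1 assessments", and HbA1c is taken from Day 1. The risk set needs no diabetes history, HbA1c below 6.5%, and participants who "had baseline fasting plasma glucose <126 mg/dL prior to the start of study treatment". New onset means any one of four components (a diabetes TEAE, two consecutive high fasting glucose values, starting an anti-diabetic drug, or one HbA1c of at least 6.5%), and it is summarised by treatment and Part. "The time (weeks) to new-onset diabetes will be calculated from the date of the first administration of study drug".

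Part 2 data begin after the Day 360 dose and are shown in two columns, inclisiran-inclisiran and placebo-inclisiran (SAP 2.1). Adverse events follow a different rule: Part 2 TEAEs are those starting after the Day 360 dose, or "AEs that were present prior to the Day 360 dosing time but increased in severity in Part 2" (SAP 2.8).

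**The concern.** For the placebo-inclisiran group, the start of Part 2 is also the start of inclisiran. A reader will take a Part 2 count of new-onset diabetes in that column as diabetes arising on the drug, and the time to onset as time on the drug. Neither follows from the rules, because both are anchored before or at the first placebo injection. The SAP moves the anchor to Day 360 for adverse events but not for this analysis.

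Diabetes is a named monitoring topic (Protocol 10.2.3), and Part 2 is meant to supply additional long-term safety data (Protocol 4.3). At stake is whether a small descriptive count attributes placebo-period findings to inclisiran. A milder form of the same question applies to the Part 2 shift and notable-value tables. Protocol 12.5.2 planned the laboratory versions for Part 1 and overall, where a Day 1 baseline raises no attribution problem; the SAP splits them by Part.

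**Working it through.** The plan gives no figure on this point, so there is none to reproduce. The check applies the rules as written.

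**Inputs.** First study drug is on Day 1 and first inclisiran for the placebo arm on Day 360 (SAP 1.1). Part 2 data start after the Day 360 dose (SAP 2.1). Fasting glucose and HbA1c are scheduled in Part 2 on Days 450, 510, 630 and 720 (Protocol Tables 8-1 and 8-3). Enrolment was 141 at 2:1 (SAP 1.1).

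**1. Diabetes count.** Take a hypothetical placebo participant with no diabetes history, normal fasting glucose, and HbA1c of 5.6% at Day 1, 6.6% later in Part 1 and 6.6% in Part 2.
- Risk set: 5.6% is below 6.5%, so the participant is included.
- Part 1: 6.6% meets the HbA1c component and counts under placebo.
- Part 2: 6.6% meets it again and counts under placebo-inclisiran. No readable rule removes a participant who already qualified in Part 1.
- With a risk set taken just before the Day 360 injection, the participant would not be counted in Part 2.

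The glucose component works the same way. The TEAE component does not carry over, because of the Day 360 reset. The medication component is unclear for a drug started in Part 1 and continued. Any one component suffices, so the reset of one does not protect the total.

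**2. Time to onset.** For an onset first occurring on Day d of Part 2, the SAP time is (d − 1)/7 weeks and time since first inclisiran is (d − 360)/7 weeks. The difference is always (360 − 1)/7 = 359/7 = 51.3 weeks.

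| Onset day | SAP time (weeks) | Since first inclisiran (weeks) |
|---|---|---|
| 450 | 449/7 = 64.1 | 90/7 = 12.9 |
| 510 | 509/7 = 72.7 | 150/7 = 21.4 |
| 630 | 629/7 = 89.9 | 270/7 = 38.6 |
| 720 | 719/7 = 102.7 | 360/7 = 51.4 |

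**3. Notable values.** Take a heart rate of 80 at Day 1, 98 in Part 1 and 97 in Part 2, against the SAP Table 5-3 limit of above 95. Baseline is not notable and both later values are, so the participant counts in both Parts. As change since study entry, that is correct. As a finding arising on inclisiran, it is not.

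**4. Size per case.** With an exact 2:1 split, 141/3 = 47 placebo participants. If all enter Part 2, one carried-over case adds 1/47 = 2.1 percentage points; for 49 down to 42 participants, 1/49 = 2.0 to 1/42 = 2.4 points.

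**5. Number of cases.** The documents give no rates. Suppose a share a of placebo participants develops a given abnormality in Part 1 and a share r of those still has it after Day 360. The expected carry-over is 47 × a × r. For a = 2%, r = 25% this is 0.2 participants; for a = 20%, r = 90% it is 8.5. Both shares are assumptions, and the range is too wide to serve as an estimate.

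**The case against.** The strongest reply is that Day 1 is a deliberate reference. SAP 2.1.1 names Part 2 explicitly, and the laboratory and vital-sign sections apply it consistently. The SAP never describes Part 2 shift or notable-value counts as new on inclisiran. This stands. A reader might infer that the Day 1 baseline in those tables is an error to be replaced; the documents do not support that, because change since study entry is a legitimate quantity. Replacing the baseline in one column would also set about one year of change in growing adolescents beside about two in the other.

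Second, Protocol 8.4.4.5 requires new onset of diabetes to be reported as an adverse event at the same HbA1c and fasting-glucose thresholds, and Part 2 TEAEs are reset at Day 360. The SAP therefore already yields a diabetes count referenced to the switch. This stands as partial mitigation, but it depends on investigator reporting and does not alter the four-component count or its clock.

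Third, onset happens once, so assigning it to the Part in which it occurred is a natural reading. The SAP is silent, and so the claim is only that a case can be counted again. Applied literally, however, the stated rule counts it.

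Fourth, the timing offset is a known constant that a reader can subtract. That is true, and it applies only to onsets first occurring in Part 2. It would be wrong to infer that every onset in the group is timed 51.3 weeks too long: a Part 1 onset on placebo has no time since inclisiran.

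Finally, the outputs are descriptive, and by-visit summaries and listings allow onset to be traced. Table shells, which are not in these documents, may carry footnotes. This limits the harm but does not correct the tabulated count.

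**Conclusion.** The point holds for new-onset diabetes in the Part 2 placebo-inclisiran column. The risk set and time origin precede the first inclisiran dose, so a persisting HbA1c or glucose finding that began on placebo can be counted as new onset in Part 2, and Part 2 onsets are timed 51.3 weeks longer than time since first inclisiran. The offset follows from the schedule alone. The count effect depends on how many placebo-period findings persist, which is unknown; the 2.1 points per case assumes 47 participants in the column.

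For laboratory shifts, notable laboratory values and notable vital signs, the conclusion is narrower. The Day 1 reference is valid, but for this group the counts include abnormalities that began on placebo and should not be read as emerging on inclisiran.

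Nothing here touches the randomized Part 1 comparison, efficacy, the TEAE definition, or the inclisiran-inclisiran column, for which Day 1 is already the last reference before inclisiran. The change is worth making because it corrects an attribution in safety tables at little cost; it does not show that the Part 2 safety results are misleading overall.

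**What to change.** 1. **Diabetes, Part 2, placebo-inclisiran.** Remove from the risk set anyone who met the definition in Part 1. Count only components first met after the Day 360 injection, including anti-diabetic medication started after it. Measure time to onset from that injection. State how a consecutive glucose pair that straddles the injection is treated.

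2. **Shift and notable-value tables, Part 2.** Keep the Day 1-referenced tables as planned and label the baseline. Add a supplementary placebo-inclisiran table that uses the last value before the Day 360 injection. The data are already scheduled: vital signs and limited chemistry on Day 360 before the injection, covering every chemistry test in SAP Table 5-1, and hematology and the other full-chemistry tests on Day 330. Do not pool this table with the inclisiran-inclisiran column or compare it directly, because time from baseline differs (about one year against two).

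The cost is a few SAP sentences, one derived baseline flag and a few extra outputs, with no new data. The hematology baseline would be about 30 days before the injection. A participant already notable at Day 360 who later worsens would appear only in the retained Day 1 table, which is a reason to keep it. If the Part 2 database is already locked, the same outputs can be issued as labelled post-hoc supplements; the SAP's covering appendix already records post-hoc analyses.
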